As described in [Section 5.6.4](#), accumulating evidence indicates a minority of patients treated with immunotherapy may derive clinical benefit despite initial evidence of progression per RECIST ([Appendix 3](#)). Therefore, in order to ascertain whether true progression has occurred, or whether a treatment mediated inflammatory/immune mediated antitumor reaction (pseudoprogression) might have preceded a tumor response, patients with apparent progression who have no additional conventional treatment options may continue study treatment and complete the subsequent disease assessment on schedule, provided the following criteria are met:

- Investigator-assessed clinical benefit. The assessment of clinical benefit should take into account whether the patient is clinically deteriorating and unlikely to receive further benefit from continued treatment.
- Patient is tolerating study drug.
- All decisions to continue treatment beyond initial progression must be discussed with the Celldex Medical Monitor and the patient, and the patient must sign an informed consent form for continued treatment after initial progression. Patients can only continue study treatment beyond initial progression if they have no additional conventional treatment options.

- Patients should discontinue study therapy upon further evidence of further progression, defined as an additional 10% or greater increase in tumor burden volume from time of initial progression (including all target lesions and new measurable lesions). For this assessment, new lesions are considered measurable at the time of initial progression if the longest diameter is at least 10 mm (except for pathological lymph nodes, which must have a short axis of at least 15 mm). Any new lesions considered non-measurable at the time of initial progression may become measurable and therefore included in the tumor burden measurement if the longest diameter increases to at least 10 mm (except for pathological lymph nodes, which must have an increase in short axis to at least 15 mm).
- For statistical analyses that include the investigator-assessed progression date, patients who continue treatment beyond initial investigator-assessed, modified RECIST 1.1 defined progression will be considered to have investigator-assessed progressive disease at the time of the initial progression event.

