10.1.4. Disease Assessment Visits

Tumor assessments will be performed every 6 weeks (± 1 week) for the first 6 months and every 9 weeks (± 2 weeks) thereafter, until documented progression of disease or initiation of alternate anticancer therapies. Patients who discontinue treatment in the absence of progression will continue to have tumor assessments until documented progression or initiation of alternate anti-cancer therapies.

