For Cohorts 2 and 3, in cases of apparent progression that may reflect enhanced inflammation and/or an initial imbalance in the kinetics of tumor growth and anti-cancer immune activity, continued combination treatment may be allowed with consent of the patient and permission granted from the Celldex Medical Monitor, until a second radiologic confirmation of progression performed at the next scheduled disease assessment (or sooner if clinically indicated). In addition, the following criteria must be met: 1) the patient experiences Investigator-assessed clinical benefit; and 2) the patient is tolerating the study treatment. Refer to Appendix 1 for the detailed schedule of assessments.

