2.2.3 Exploratory endpoint(s)

Efficacy

- Immune-related RECIST ORR and PFS (Cohorts 2 and 3)

Correlative:

- Concentration of antibody-drug conjugate(ADC), total antibody (TA), and free Monomethyl auristatin E (MMAE).
- Pharmacodynamic parameters, including gpNMB expression levels and other biomarkers in serum and both normal and tumor tissue; localization of glebatumumab vedotin, CR011, or MMAE at the tumor site; evaluation of tumor infiltrating and peripheral leukocytes, circulating tumor cells, and other immune response cells of interest. Additional analysis may include immune response assessment to potentially relevant tumor antigens.

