5 GENERAL CONSIDERATIONS

Analysis datasets will be created according to Clinical Data Interchange Standards Consortium CDISC/Analysis Data Model (ADaM) standards. SAS v9.4 or higher software will be used to perform all data analyses (ADaM datasets, tables, figures, and listings).

Baseline will be defined as the most recent non-missing value prior to or on the same day of the first dose of glembatumumab vedotin. Generally, only pre-specified planned visits will be used in the by-visit summaries, statistical analyses and calculations of any derived safety parameters except for lab summary tables. All post baseline measurements including scheduled and unscheduled assessments will be used to derive the worst / best assessment for lab summary tables.

The primary response criterion is RECIST 1.1. Confirmation of response is required in defining best overall response (BOR) as the primary endpoint. The irRECIST is used as a secondary analysis for all efficacy endpoints except for OS.

All analyses specified in this plan will be performed by cohort. All baseline tables will include a column for each cohort and a column for overall. Unless otherwise stated, continuous variables will be summarized with n, mean, median, standard deviation, Q1, Q3, minimum and maximum, and categorical variables will be summarized with frequency counts and percentages.

Unless otherwise stated, all listings will be sorted by cohort, subject number, and then by visit date if applicable.

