8 EFFICACY ANALYSES

8.1 Analyses of the Primary Endpoint

The primary endpoint is objective response rate (ORR). ORR will be estimated based on the proportion of evaluable subjects who achieve best overall response (BOR) of complete response (CR) or partial response (PR) per RECIST 1.1 that are confirmed at an interval of at least 28 days. The estimate of the objective response rate will be accompanied by one-sided and two-sided 95% Clopper-Pearson confidence intervals. For Cohort 1, a one-sample exact binomial test with one-sided significance level of 0.05 will be used to test the response rate under the null (H_0 : ORR=5%) and alternative (H_a : ORR=15%) hypotheses (5% vs. 15%, respectively). For each of Cohorts 2 and 3, the estimate of ORR will be compared with the fixed rates of 5% and 10% with one-sided significance level of 0.10. The primary ORR analysis is based on evaluable population and secondarily on Safety Population. The analysis of ORR will also be summarized for the PP population.

In this study, a minimum interval of 5 weeks from first dose date is required for stable disease (SD) status. Subjects with Not Evaluable (NE) or missing response will be treated as non-responders (i.e., they will be included in the denominator when calculating ORR).

Secondary analyses of ORR will include responses observed at a single time point (i.e., analysis of ORR will be summarized based on confirmed and unconfirmed CR or PR) based on Safety Population.

Waterfall plots will be used to depict graphically the maximum percent decrease from baseline in the sum of longest diameters of target lesions. A spider plot will be generated to depict changes in the sum of longest diameters of target lesions over time. A swimmer plot will also be used to show the effect of study treatment on tumor response for individual subjects.

Tumor assessment data after initiation of other anticancer therapy will be excluded for response related efficacy endpoints including BOR, DOR, PFS, waterfall plot, spider plot and swimmer plot.

For Cohorts 2 and 3, supplementary analyses of tumor response and progression will be performed using irRECIST criteria (in which new lesions do not necessarily constitute progression, but contribute to the calculated sum of diameter of all measurable disease). To be noted, if not all target lesions are measured at a visit, the sum of diameters should not be calculated.

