8.2 Analyses of Secondary Endpoints

8.2.1 PFS

Progression Free Survival (PFS) is defined as the time from the study treatment first dose to the earlier of disease progression or death due to any cause. Disease progression will be assessed using RECIST 1.1. The progression and censoring dates will be based on the May 2007 FDA Guidance for Industry, ‘*Clinical Trial Endpoints for the Approval of Cancer Drugs and Biologics*’. Determination rules for events or censored PFS is summarized in Table 2.

Table 2: Date of Event or Censoring for the Primary PFS analysis

Situation	Date of Event or Censoring	Outcome
Disease progression between scheduled disease assessments	Date of progression	Event
Death between scheduled disease assessment	Date of death	Event
Death before the first planned disease assessment at 6 weeks (plus 1 week window) without any disease assessment	Date of death	Event
No baseline disease assessments	Date of first dose	Censored
No post-baseline disease assessments without death before the first planned disease assessment	Date of first dose	Censored
Discontinuation of study treatment without progression (i.e., due to toxicity, withdrew consent, or lost to follow-up) and no further radiographic assessment ^a	Date of last radiological assessment	Censored
Alternate anticancer treatment started without documentation of disease progression beforehand ^b	Date of last radiological assessment prior to start of further anticancer treatment	Censored
Death or disease progression after missing two or more consecutively scheduled disease assessments ^c	Date of last radiological assessment without documented progression disease prior to death/progression	Censored
Patients who have not progressed and are alive	Date of last radiological assessment without documented progression disease	Censored

- For a patient who discontinues study treatment without PD and continues to have radiographic assessments, post-treatment radiographic assessments will be considered for PFS analyses according to the rules in this table.
- Alternate anticancer treatment interventions that are diagnostic (e.g. biopsy) or palliative (e.g., local radiation for painful nodule), as determined by medical review, will not routinely require censoring unless they are determined to interfere with the assessment of the patients’ disease status.

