13. The End of Treatment Visit should be performed within 28 days after last dose of study treatment and prior to initiation of alternate therapies.
14. Disease assessments will be performed every 6 weeks (\pm 1 week) for 6 months and every 9 weeks (\pm 2 weeks) thereafter, scheduled based on the first dose of glembatumumab vedotin at CID1, until documented progression of disease or initiation of alternate anticancer therapies. For Cohorts 2 and 3, in cases of apparent progression that may reflect enhanced inflammation and/or an initial imbalance in the kinetics of tumor growth and anti-cancer immune activity, continued combination treatment may be allowed with permission granted from the Celldex Medical Monitor, until a second radiologic confirmation of progression performed at the next scheduled disease assessment (or sooner if clinically indicated) (Protocol [Section 5.5.3](#) and Protocol [Section 7.2.4.1.1](#)). If a partial or complete response is noted, a follow-up disease assessment must be done no sooner than 28 days later to confirm response. Patients who discontinue treatment in the absence of progression will continue to have tumor assessments until documented progression or initiation of alternate anti-cancer therapies. If surgical intervention or localized radiation are indicated (either for palliation or down-staging of previously non-resectable tumor), these interventions should be avoided if clinically feasible until after the 12-week response assessment. Prior to any intervention (such as surgical resection, palliative radiation or alternate anti-cancer therapy), every effort should be made to perform a tumor response assessment in order to document progression and/or confirm an objective response. Patients who undergo surgical resection or radiation in the absence of progression may continue to receive study treatment until remaining lesions meet criteria for progression of disease.

15. Subsequent to disease progression, all patients will be followed at 12 (±2) week intervals until study closure. Patients who discontinue treatment in the absence of progression will continue to have tumor assessments until documented progression or initiation of alternate anti-cancer therapies. These visits may be performed by telephone.

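### irRECIST PFS and DOR are planned without their own event rule, and carrying the PFS censoring rules across would informatively censor progressors who are not re-scanned

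*SAP*

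**What the plan says.** **Planned analyses.** SAP section 5: "The irRECIST is used as a secondary analysis for all efficacy endpoints except for OS". SAP 2.2.3 lists irRECIST ORR and PFS as exploratory endpoints for Cohorts 2 and 3. SAP 8.2.2 adds irRECIST DOR for the same cohorts. SAP 8.1 describes the criteria as ones "in which new lesions do not necessarily constitute progression, but contribute to the calculated sum of diameter of all measurable disease".

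**Scanning.** Protocol 10.1.4 schedules tumor assessments "until documented progression of disease or initiation of alternate anticancer therapies". Protocol 7.2.4.1 makes RECIST 1.1 the criterion that ends the assessment visits. After that, SAP 16.1 says: "Subsequent to disease progression, all patients will be followed at 12 (±2) week intervals until study closure"; these contacts may be by telephone. SAP 8.1 drops tumor data obtained after a new anticancer therapy.

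**Exception.** In the combination cohorts, treatment may continue past apparent progression to a second scan. This needs patient consent, the medical monitor's permission, clinical benefit and tolerance (SAP section 1). Protocol 7.2.4.1.1 adds: "Patients can only continue study treatment beyond initial progression if they have no additional conventional treatment options".

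**Censoring.** Protocol 11.5.1 names RECIST 1.1, plus irRECIST for Cohort 2, as the progression criteria for PFS, then gives one censoring list for both. SAP 8.2.1 names RECIST 1.1 only, and the title of its Table 2 confines it to the primary PFS analysis. Its row "Patients who have not progressed and are alive" censors at the last scan without progression. SAP 8.2.2 ties DOR censoring to the PFS rules and then plans DOR by irRECIST.

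**The concern.** A new lesion is progression under RECIST 1.1 but not automatically under irRECIST. It therefore ends routine scanning without necessarily being an irRECIST event. If the patient is not allowed to continue treatment, no later scan exists to show irRECIST progression. Under the PFS rules the RECIST progression scan becomes the last scan without progression, and the patient is censored there. Starting a new therapy leads to the same date.

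Kaplan-Meier estimation then assumes that these patients go on to progress at the same rate as those still under observation. They have just progressed by RECIST, and those who were deteriorating or had other treatment options are the ones not re-scanned. The curve is pushed upward. A reader comparing irRECIST PFS with RECIST PFS could take the gap as delayed immune benefit when part of it comes only from the end of follow-up.

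**Working it through.** **Plan figures.** No event count, power or rate is given for irRECIST PFS, so there is nothing to reproduce. The only PFS calculation in the plan concerns RECIST PFS in Cohort 1, and it does reproduce: (1.2816 + 0.8416)² / (35² × ln(0.99)²) = 4.508 / 0.1237 = 36.4 events, against 36 stated.

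**Inputs from the documents.** Scans at weeks 6, 12, 18 and 24, then every 9 weeks. A death is an event unless it follows two or more missed assessments (SAP Table 2). About 30 patients per cohort.

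**Assumptions.** Exponential PFS with median 9, 13 or 20 weeks. A share p of progressions (10% to 40%) is RECIST progression without irRECIST progression at that scan. A fraction f of those (0 or 30%) is re-scanned. Median survival after progression is 26 weeks. With full scanning, irRECIST progression would be seen at the next scan.

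**Comparator.** irRECIST PFS exceeds RECIST PFS by definition, so the bias must be measured against irRECIST PFS with full scanning.

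**Hand check: 13-week median, f = 0, every such patient censored at the progression scan.**
- Chance of progression in a 6-week interval: 1 − 2^(−6/13) = 0.2738.
- RECIST PFS at week 26, after four scans: 0.7262⁴ = 27.8%.
- Full-scan irRECIST PFS adds the share p of week-24 progressors still alive at week 26. These are 0.7262³ × 0.2738 × 2^(−2/26) = 0.0994 per unit of p. Result: 29.8% at p = 20% and 31.8% at p = 40%.
- Censored version: (1 − 0.2738 × 0.8)⁴ = 37.2% at p = 20%, and (1 − 0.2738 × 0.6)⁴ = 48.8% at p = 40%.
- Overstatement: 7.4 and 17.0 points.

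**Simulation on the scan grid, 20,000 patients per scenario, 13-week median, 26-week rates.** The last two columns bracket the effect of new therapy. In the first, nobody starts one, so deaths before two missed assessments are events. In the second, all are censored at the progression scan.

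| p | f | RECIST PFS | Full-scan irRECIST PFS | Censored, early deaths as events | All censored |
|---|---|---|---|---|---|
| 10% | 0 | 27.9% | 29.1% | 31.7% (+2.6) | 32.4% (+3.3) |
| 20% | 0 | 27.3% | 29.5% | 34.5% (+5.0) | 36.6% (+7.1) |
| 20% | 30% | 27.7% | 29.7% | 33.4% (+3.7) | 34.8% (+5.1) |
| 40% | 0 | 28.2% | 32.2% | 43.5% (+11.3) | 49.0% (+16.8) |
| 40% | 30% | 27.9% | 32.2% | 39.6% (+7.4) | 43.0% (+10.8) |

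With early deaths as events and f = 0, the other medians give similar sizes. At p = 20%: 22.8 − 18.0 = 4.8 points (9 weeks) and 50.0 − 45.4 = 4.6 (20 weeks). At p = 40%: 30.6 − 19.5 = 11.1 and 57.0 − 47.0 = 10.0.

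Over all scenarios the smallest overstatement is 17.8 − 16.2 = 1.6 points and the largest is 36.8 − 19.5 = 17.3. It is upward in every one. irDOR follows the same mechanism but was not sized.

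**The case against.** The strongest reply is that the SAP never says irRECIST PFS is to be censored this way: Table 2 is titled for the primary PFS analysis, and SAP 8.2.1 names RECIST 1.1 only. This stands as a limit on the wording for PFS. It does not remove the point. Protocol 11.5.1 applies one censoring list to both criteria for Cohort 2, SAP 8.2.2 carries the PFS rules to DOR and then plans irRECIST DOR, and no alternative rule is offered.

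A reader might infer several stronger things that the documents do not support:

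- *Scanning stops for everyone at RECIST progression.* The exception allows a second scan in the cohorts where irRECIST is used. It selects patients, however, so it reduces the problem without curing it.
- *Every new-lesion progressor is censored.* New lesions enter the irRECIST sum, so some patients are irRECIST events at the same scan.
- *Deaths disappear.* Under Table 2 a death before two missed assessments remains an event.
- *The median is inflated by 1/(1 − p), for example 1.67-fold at 40%.* That factor compares with RECIST PFS and ignores deaths. At p = 40% and a 13-week median it is the comparison 49.0 − 28.2 = 20.8 points, against 11.3 on the proper comparator with early deaths counted.
- *The irRECIST disease control rate is inflated too.* It is a proportion, with no Kaplan-Meier censoring, and is not part of this point.

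Protocol 7.2.4.1.1 dates progression at the initial event for patients treated beyond it. Whether that reaches irRECIST is unclear, and it covers only patients who continue, not those who stop.

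**Conclusion.** The point holds in this limited form. irRECIST PFS and DOR are planned, imaging after RECIST progression exists only for a selected group, and the only available rules would informatively censor the irRECIST-negative progressors who are not re-scanned. The 26-week irRECIST PFS rate would be overstated by about 2 to 17 points across the scenarios. With early deaths counted and no re-scanning, the figure is about 5 points at a 20% share and about 11 at 40%.

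The shares, the 9-to-20-week median, the 26-week post-progression survival and progression at the next scan are assumptions, not figures from the documents. If many of these patients would have stayed free of irRECIST progression beyond the next scan, the bias is smaller.

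For scale, the binomial standard error of a 29.5% rate in 30 patients is √(0.295 × 0.705 / 30) = 8.3 points. The bias is within ordinary sampling error at a 20% share and exceeds one standard error at 40%, but it always points the same way. The analysis is supplementary; the primary ORR test and RECIST PFS are unaffected. It is worth correcting because the correction is cheap.

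**What to change.** Add one SAP rule, for irRECIST PFS and DOR only. A patient with RECIST 1.1 progression and no later evaluable scan before new anticancer therapy counts as an irRECIST event on the RECIST progression date. All other Table 2 rules carry over unchanged, so ordinary censoring is not disturbed. Show the censored version as a sensitivity analysis and report the number of patients affected in each cohort.

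No extra scans are needed. The cost is a slightly conservative irRECIST PFS for true pseudoprogressors who were not re-scanned. With f = 0 the rule returns RECIST PFS, which in the table lies 29.5 − 27.3 = 2.2 points (p = 20%) or 32.2 − 28.2 = 4.0 points (p = 40%) below full scanning. The estimate stays between RECIST PFS and full-scan irRECIST PFS, so the upward bias is gone.

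Also reconcile the scope of irRECIST PFS (Cohort 2 in Protocol 11.5.1, Cohorts 2 to 5 in Protocol 11.1, Cohorts 2 and 3 in SAP 2.2.3) and its status (secondary in SAP section 5, exploratory in SAP 2.2.3).

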5.1 Pooling of Centers

Data from all study centers will be pooled together for analyses in this study.

5.2 Multiplicity Adjustment

This is an early phase exploratory study and adjustment for multiplicity is not planned.

5.3 Subgroups

Subgroup analyses will be performed to explore the correlation between degree of gpNMB expression and anti-cancer activity of glembatumumab vedotin in advanced melanoma for efficacy endpoints. Rash developed in treatment cycle 1 will also be explored as another subgroup variable. Specifically, the following subgroup analyses will be performed for ORR, PFS and OS:

- Age group (<65, >=65)
- Gender (Female, Male)
- CNS involvement (Yes, No)
- Number of disease site (<=3, >3)
- ECOG PS (0, 1)
- GpNMB Expression (<95%, >=95%)
- Rash in cycle 1 (Yes, No). The medical term of rash is to be defined by medical manual review and documented prior to analysis. Only treatment-related rash is considered. If a subject only has 1 cycle of treatment, rash onset within 21 days from the first dose will be considered as rash in cycle 1.
- Time between last prior CPI and initiation of study treatment (<=3 months, >3 months).
- Duration of last prior CPI (<=3 months, >3 months).

- Cohort 3 only: PD-L1, positive (positive in $\geq 1\%$ tumor cells) vs negative

5.4 Adjustments for Covariates

No analysis adjusting for covariates are planned for this study.

5.5 Handling of Missing Data

Partially missing date of diagnosis needs to be imputed for calculating time from diagnosis to baseline. The following imputation rules will be applied:

- If only day is missing, impute as the first day of the month.
- If both day and month are missing, impute as Jan 1st.
- If year is missing, no imputation will be performed.

The above rules also apply to other diagnosis dates including date of metastatic disease, date of advanced disease, date of cancer surgery, radiation and prior cancer medications.

For partially missing additional cancer therapy date, the imputation is same as above except when only day is missing and the month is the same as in on-study progression date, in which case the day of additional cancer therapy will be imputed as the day of progression + 1 to avoid censoring a progression event due to an uncertain anticancer therapy start date.

For partially missing AE start dates (missing day and/or month), the following imputation rules will be applied:

- If both day and month of the AE start date are missing, the day and month will be imputed with the day and month of the first study dose date if the year is equal to the year of the first dose given the AE end date is not prior to first dose. Otherwise, the month and day is imputed as the first day of the year (Jan 1st).
- If only day is missing, and if the year and month are equal to the first dose date, the AE start date will be imputed as the first dose date given the AE end date is not prior to first dose. Otherwise, the day will be imputed as “01”. As a general consideration, imputed AE start date cannot be after AE end date if available.

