7.3 Prior Therapy and Medical History

Prior medical and surgical history will be coded by MedDRA (Medical Dictionary for Regulatory Activities) and will be summarized by treatment cohorts.

The following prior anti-cancer treatment parameters will be summarized:

- Number of prior systemic anti-cancer regimens
- Prior cancer treatment class: check point inhibitor (CPI) with subcategories including CTLA-4 and PD-1/PD-L1, other immunotherapy, BRAF related TKI, cytokines and cytotoxic-containing therapy
- Number of prior CPI containing regimens
- Best response to first prior CPI treatment
- Best response to and duration of last prior CPI treatment
- Surgery/Biopsy description (Resection, Biopsy or Other)
- Prior radiation therapy (Yes or No)
- Prior cancer surgeries (Yes or No, biopsy excluded)
- Time from last anti-cancer therapy to first dose of glembatumumab vedotin (≤ 2 or > 2 months)
- Time from CPI as last anti-cancer therapy to first dose of glembatumumab vedotin (≤ 2 months, > 2 month to ≤ 6 months, or > 6 months)

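### SAP 5.5 imputes partial prior-CPI dates to the earliest day without separating start from stop dates, so the gap since last CPI is overstated and CPI duration can come out negative

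*SAP*

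**What the plan says.** SAP 5.5 opens with the purpose of the rule: "Partially missing date of diagnosis needs to be imputed for calculating time from diagnosis to baseline". Two instructions follow: "If only day is missing, impute as the first day of the month" and "If both day and month are missing, impute as Jan 1st". If the year is missing, nothing is imputed. The section then carries these rules over to a list of further dates that ends with the "date of cancer surgery, radiation and prior cancer medications". A medication has a start and a stop date, but the list does not distinguish them, and no other part of either document gives a rule for partial stop dates of prior therapy. The only order check in SAP 5.5 is for adverse events, where an imputed start may not fall after a known end.

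These dates feed planned analyses. SAP 5.3 states that "the following subgroup analyses will be performed for ORR, PFS and OS", and the list includes "Time between last prior CPI and initiation of study treatment (<=3 months, >3 months") and "Duration of last prior CPI (<=3 months, >3 months"). SAP 7.3 tabulates the duration of the last CPI, "Time from last anti-cancer therapy to first dose of glembatumumab vedotin" (cut at 2 months), and the interval from a CPI given as last therapy (cut at 2 and 6 months).

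**The concern.** For a diagnosis date, the earliest possible day is a common convention. For a stop date it is a one-sided error. The imputed stop can only move back in time, so the interval from last CPI to first dose can only grow. Where the start date is better known than the stop date, CPI duration can only shrink, and nothing prevents an imputed stop from falling before a recorded start.

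Prior CPI exposure defines the study population. The two subgroups ask whether activity differs by how recently, and for how long, a CPI was given. A rule that moves recent-CPI patients into the longer-gap group, and never the reverse, distorts that comparison in a predictable direction.

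**Working it through.** The plan states no figure that depends on this rule, so there is none to reproduce. The check is date arithmetic followed by an illustrative simulation.

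**Size of the shift (calendar year 2016, 366 days).** Error = true date − imputed date.
- Day missing: mean of (day of month − 1) = (7×465 + 4×435 + 406)/366 = 5401/366 = 14.8 days, range 0 to 30.
- Day and month missing: mean of 0 to 365 = 66,795/366 = 182.5 days, range 0 to 365.

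**Worked cases.** Duration = stop − start + 1. The cut is taken as 3 × 30.4375 = 91.3 days; the SAP does not define a month in days here.
- Gap: true stop 30 Mar 2016, recorded without the day; first dose 20 Jun 2016. True gap 82 days, imputed gap 111. The patient moves from at most 3 months to more than 3 months.
- Duration: start 20 Dec 2015, same stop. True duration 102 days, imputed 73. The patient moves the other way.
- Negative, day missing: start 10 Mar 2016, stop recorded as March 2016. Imputed stop 1 Mar, duration −8 days.
- Negative, year only: start 10 Feb 2016, true stop 30 May 2016 recorded as 2016. True duration 111 days, imputed −39.

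**Simulation, per patient with a partial date (100,000 draws per row).** Assumptions not in the documents: first dose uniform over a year, true gap uniform over 28–180 days, true CPI duration uniform over 21–365 days. The lower end of the gap reflects the 4-week antibody washout in Protocol 7.2.2.2.

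| Partial date | Mean duration error (days) | Duration ≤0 | Wrong duration subgroup | Mean gap error (days) | Wrong gap subgroup |
|---|---|---|---|---|---|
| Stop: day | −14.8 | 0.5% | 4.4% | +14.8 | 9.7% |
| Stop: day and month | −182.3 | 47% | 50% | +182.3 | 38% |
| Both: day | 0.0 | 0% | 4.2% | +14.7 | 9.6% |
| Both: day and month | −0.2 | 0% | 33% | +182.3 | 38% |
| Start only: day | +14.7 | 0% | 4.3% | 0 | 0% |
| Start only: day and month | +181.9 | 0% | 19% | 0 | 0% |

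With true gaps of 28–365 days, the wrong-gap share for a partial stop falls to 4.5% (day missing) and 17% (year only). All gap errors come from patients whose true gap is at most 91 days. That is 64 of the 153 possible values in the 28–180 range, so among those patients the shares are 0.097/(64/153) = 23% and 0.381/(64/153) = 91%.

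**Would last-day imputation cure it?** This was tested with the stop date set to the last day of the month or 31 December, capped at the day before first dose, and a complete start date.
- Day missing: gap error −14.7 days, 9.5% in the wrong gap subgroup.
- Year only: gap error −85.7 days, 51% wrong, against 38% under the SAP rule. Negative durations disappear, and wrong duration subgroups fall from 50% to 17%.
- If both dates are partial, pairing an earliest start with a latest stop overstates duration by about 30 days (day missing) or 267–312 days (year only), where the SAP rule averages about zero.

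**Bounding instead of imputing.** In the gap case above, the stop lies between 1 and 31 March, so the gap lies between 111 and 81 days. It spans 91.3, so the patient is unknown. In the first negative case, the start bound leaves 10 to 31 March, a duration of 1 to 22 days, and the patient is safely at most 3 months. By construction, no classified patient is misplaced.

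**The case against.** Five arguments weigh against the point.

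- **Duration is not always shortened.** A reader might infer that the rule always understates CPI duration. It does so only when the start date is complete or less incomplete than the stop. With both dates equally partial the mean error is about zero and no duration is negative; with only the start partial, duration is overstated. The one-directional claim holds without condition only for the gap. This objection stands.
- **The text may not mean stop dates.** SAP 5.5 introduces its list as further diagnosis dates and never mentions stop dates. If it covers start dates only, stop dates have no rule, and the subgroups are undefined for patients with partial ones. The section needs correcting on either reading.
- **Recent CPI dates should be well known.** Sites must check the 4-week washout (Protocol 7.2.2.2), a pre-entry biopsy taken after the last systemic therapy (Protocol 7.2.2.1) and, in Cohort 3, continuous CPI (Protocol Table 1, footnote 23). CRF entries are checked against source (Protocol 12.1). This makes a year-only date for a recent CPI less likely, but does not remove the problem. A stop in March 2016 before a first dose on 20 June passes the washout on any day of March, yet spans the 3-month cut. A stop recorded only as 2015 before a first dose on 20 Feb 2016 gives a gap of 51 (31 + 20) to 415 (365 + 50) days: past the washout, but unclassifiable.
- **The conditional percentages look large.** The 23% and 91% apply only to patients with a true gap of at most 91 days and a partial stop date. The shares of all patients with a partial stop date are the fairer summary.
- **The stakes are limited.** SAP 5.2 describes the study as early and exploratory, without multiplicity adjustment, and no decision rule uses these subgroups. This stands and limits the weight of the point.

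**Conclusion.** The defect holds. Applied as written, the rule never understates and nearly always overstates the gap from last CPI when the stop date is partial, by a mean of about 15 days (day missing) or 182 days (year only). It shortens CPI duration, sometimes below zero, when the start date is better known than the stop.

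Under the stated assumptions, a patient with a partial stop date lands in the wrong gap subgroup with probability 9.7% or 4.5% (day missing) and 38% or 17% (year only), for true gaps of 28–180 or 28–365 days.

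The documents do not give the number of partial dates, so misclassification is a demonstrated possibility, not a known count. Taking Cohort 1's 52 evaluable patients and gaps of 28–180 days, 10% with the day missing would move 52 × 0.10 × 0.097 = 0.5 patients; the range is 0 to 5 as that share runs from 0% to 100%.

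A reader might infer that the trial's main conclusions are at risk. They are not: the primary ORR analysis, overall PFS and OS, sample size and alpha do not use these dates. The effect is confined to exploratory subgroups and baseline tables.

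**What to change.** In SAP 5.5, give stop dates of prior therapy their own rule:

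1. For CPI given before study, require start ≤ stop < first study dose. In Cohort 3, the stop is the last pre-study CPI dose.
2. For the 3-month subgroups in SAP 5.3 and the 2- and 6-month categories in SAP 7.3, derive the earliest and latest possible stop dates within those bounds, and likewise the possible start dates where duration is needed. Assign a category only if both extremes give the same one; otherwise report unknown.
3. Do not simply replace first-day with last-day imputation.

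The cost is a few sentences in the SAP and a small change to the date derivation. Some patients will be unclassified. With the day missing, the possible range is about 29.5 days wide, so the unknown share for the gap is roughly 29.5/153 = 19% for true gaps of 28–180 days (153 possible values) and 29.5/338 = 9% for 28–365 days (338 values), counted among patients with such a date. Most patients with a year-only date would be unknown, because that date does not carry the information the subgroup needs. If partial dates prove rare, the change costs almost nothing.
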